RCT. The final phase of the proposed project will implement an RCT to examine whether the program is feasible and associated with improvements in the treatment targets (see Measures and Figure 1). Thirty-six siblings will be recruited and randomly assigned to participate in Siblings FORWARD (N=18) or receive written materials about future planning (N=18). Siblings assigned to Siblings FORWARD will complete Time 1 (pre-program) measures, participate in the 6-session intervention over 4 months, complete Time 2 measures immediately after program completion, and complete Time 3 measures 3 months later. Those assigned to the control condition will complete Time 1 measures at the time of enrollment, Time 2 measures 4 months after enrollment, and Time 3 measures 7 months after enrollment. With the exception of the clinician rating of the sibling's ASD symptoms (see Measures), all data will be collected by the Boston University study team via home visits in order to separate data collection from the Arc providers. Adults with ADS and their families will determine whether the adult with ASD can complete the questionnaires (see Methods). When possible, the adult with ASD will complete the measures independently in the presence of a Boston University research team member. These measures can also be completed with the support of a research team member, sibling, parent, or service provider. Given possible geographic separation, sibling data will be collected via mailed questionnaire packets. We will track this data collection method to inform future data collection logistics.

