**Control Condition.** Currently, the standard of care is minimal sibling involvement in future planning or therapeutic activities for their brother/sister with ASD. Some organizations have created resources targeted toward parents (e.g., the Arc's Build Your Plan™ tool), but our preliminary data show that these resources are often perceived by siblings to be minimally helpful and/or overwhelming, which serves to increase their anxiety and decrease the likelihood that they will take action. Several organizations have recently published "tip sheets" for siblings who wish to have a larger role in future planning. The extent to which these tip sheets are accessed by siblings or helpful as standalone resources is unknown, but they are frequently the only resource available to siblings. Given that tip sheets are inexpensive and easy to create and disseminate, it will be important for the proposed project to demonstrate that the outcomes of the Siblings FORWARD program warrant the extra time and resources. Therefore, the control condition will involve providing the same tip sheets and packet of information about resources for adults with ASD as those distributed in Session 3 of the Siblings FORWARD program. After all outcome data are collected from the program and control groups, siblings in the control condition will be offered the opportunity to participate in the Siblings FORWARD program.

**Telehealth Technology. Rationale:** The Siblings FORWARD program will be delivered via synchronous videoteleconferencing (VTC) technology. VTC technology enables the secure delivery of interactive meetings that incorporate audio and video streams of data across multiple sites. The considerable growth of VTC interventions over the last few years has been bolstered by technological advances in VTC, portability of the technology, decreased costs, and increased internet access and technological literacy of the general population. This approach has been employed to overcome geographical barriers to care, which has led to increased availability, accessibility, and acceptability of mental health care delivered remotely. Although most telehealth research focuses on individuals, recent work supports the feasibility of family-based telehealth.

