#### Program Targets: Sibling Future Planning Knowledge & Skills (Measured at Time 1, Time 2, & Time 3)

1. Problem Solving Skills. Siblings will complete the Social Problem-Solving Skills Inventory-Revised (SPSI-R). This 52-item self-report measure was used in a problem-solving intervention with mothers of children with ASD. Five dimensions assess how the individual strategically approaches a situation (positive problem orientation, negative problem orientation, rational problem solving, impulsivity carelessness style, and avoidance style). Siblings will rate the extent to which each item is 1 (not at all true) to 5 (extremely true) of them. Higher scores indicate better problem-solving skills. Good reliability is reported.
2. Family Communication about Future Planning. Siblings will rate the frequency with which they have had family discussions about planning for the future of their brother/sister with ASD. Siblings will respond to a 1-item measure previously used in a study evaluating a peer-support program for aging caregivers of adults with intellectual and developmental disabilities. The item is scored on a 3-point scale (not discussed at all, discussed somewhat, discussed a great deal).
3. Future Planning Self-Efficacy. We will adapt the Caregiving Self-Efficacy Scale that has been used by with parents and adult siblings to evaluate participation in a peer-support intervention for aging caregivers. The scale consists of 6 items rated on a 4-point scale (strongly disagree to strong agree). Sample items include: I honestly believe I can be a good caregiver to my relative; If anyone can find the answer to what is troubling my relative, I can. The scale has good reported reliability (alphas .73-.82).
4. Sibling Barriers to Future Planning. Siblings will complete a list of barriers to future planning adapted from a measure used by Heller and Caldwell. The original list included 12 barriers such as: difficulty finding helpful contact persons within the service system, emotional barriers involved with thinking their parents' mortality, or disagreement with a relative with a disability about the future.
5. Knowledge of adult services and delivery systems. Siblings will rate their knowledge of the services received or needed by their brother/sister with ASD. We will use a list of 12 adult services: physical

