*Aim 3: To assess the outcomes of participation in the Siblings FORWARD program.* We will examine whether the program shows promise of being successful with the intended population by conducting two-way repeated measures ANOVAs examining main effects of intervention condition (Siblings FORWARD vs. control) and repeated for assessment (pre- post- and 3-month follow up) on measures for program targets (sibling problem solving skills, family communication, future planning self-efficacy, barriers to future planning, and knowledge of services and family future plans) and proximal outcomes (sibling plan of action and adult with ASD quality of life, perceptions of unmet needs, and family relationships). Post-hoc tests will be used in multiple comparisons between groups and within each group. Effect sizes (Cohen's d) will be calculated using the mean difference of the changes recorded from pre- to post-program. We will also analyze percent change and reliable change. If data are missing, analyses will be performed using the 'last observation carried forward' method for intention-to-treat analysis. We will examine descriptive statistics (mean, SD, confidence intervals) at the participant level for patterns and direction of change on outcome measures. We will conduct intent-to-treat analyses if there is program attrition. Finally, we will examine benefit of the program to control participants who elect to participate in the Siblings FORWARD program using one-way ANOVAs (pre to post-program) on treatment targets and proximal outcomes.

We will conduct a preliminary investigation of potential moderators of program effectiveness, including characteristics of the sibling (BAP), family (income, race/ethnicity, English as the primary language, number of family members with ASD), and adult with ASD (severity of ASD symptoms, problem behaviors, functional independence). We will calculate correlations between these variables and change scores in primary outcome variables, and independent samples t-tests between these variables and program completion status.

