**Table 4: Timeline & Milestones**

Table 4: Timeline & Milestones		
Y1	Jan-Mar	
 
- Convene CAB to review qualitative goals
 
- Hire & train staff
 
- Finalize recruitment procedures
 

	Apr-June	
 
- Recruit & conduct focus groups/interviews with service providers (N=12-16), siblings (N=18-24), & adults with ASD (N=8)
 
- Analyze qualitative findings
 
- Finalize program manual by incorporating qualitative findings & CAB input
 
- Set up WebEx technology
 

	July-Dec	
 
- Provide in-depth training on program delivery to providers
 
- Conduct open trial (N=5)
 
- Provide ongoing, intensive consultation to community providers
 
- Collect, analyze, & iteratively implement feasibility & acceptability data from open trial participants & providers
 

Y2	Jan-Dec	
 
- Implement the RCT by enrolling ~2 families per month (24 siblings)
 
- Prepare conference papers & manuscripts from qualitative data
 

Y3	Jan-June	
 
- Continue RCT by enrolling ~2 families per month (12 additional siblings)
 

	July-Sept	
 
- Finish collecting 3-month follow-up data
 
- Offer Siblings FORWARD program to control siblings
 

	Oct-Dec	
 
- Collect post-program data for control sibs who later enrolled in Siblings FORWARD
 
- Conduct quantitative & qualitative analyses from RCT
 
- Revise and finalize program manual
 
- Prepare conference papers & manuscripts
 
- Prepare grant application for a larger-scale trial of the program
 

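### The pre-to-post analysis of control siblings who later take the program is named as a one-way ANOVA and not stated to be within-person; run as an ordinary one-way ANOVA it would ignore the pairing

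*Combined protocol and SAP*

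**What the plan says.** The Aim 3 part of Data Analysis describes two ANOVAs in one paragraph.

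- For the randomised comparison it specifies "two-way repeated measures ANOVAs examining main effects of intervention condition", with assessment (pre, post and 3-month follow-up) as the repeated factor.
- For the later use of the program by controls it says "we will examine benefit of the program to control participants who elect to participate in the Siblings FORWARD program", and the method is "using one-way ANOVAs (pre to post-program) on treatment targets and proximal outcomes".

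The Control Condition paragraph says that, once all outcome data are in, "siblings in the control condition will be offered the opportunity to participate in the Siblings FORWARD program". The RCT procedures put 18 siblings in the control arm. Table 4 places the offer in July to September of Year 3. For October to December it lists one data task for this group: "Collect post-program data for control sibs who later enrolled in Siblings FORWARD". It lists no new pre-program assessment for them.

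The documents give no pre-post correlation, SD, significance level or power for this analysis.

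**The concern.** Pre and post values come from the same siblings. With two time points, an ordinary one-way ANOVA on time is the independent-samples t-test in another form. Its error term contains the stable differences between siblings, which cancel in a within-person comparison. Because the main analysis is explicitly repeated measures and this one is not, an analyst who follows the text literally could run the unpaired test.

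At stake is precision in a very small group. Intervals would be wider than the data justify, and a real change could be reported as no evidence of change. The plan uses Aim 3 to judge whether the program shows promise, and Table 4 has a larger grant application following it, so a needlessly uninformative result has some cost.

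A second gap sits beside the first: the plan does not say which assessment counts as the pre-program value for these siblings.

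**Working it through.** The plan states no figure for this analysis, so there is nothing to reproduce. The check shows what the unpaired reading would cost.

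**Inputs from the documents.** Same siblings pre and post (Data Analysis, Aim 3). At most n = 18 (RCT procedures), probably fewer because participation is elective.

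**Assumed inputs.** Equal variance s² at both times and pre-post correlation r, shown over a range. For the power illustration only: normal data, a two-sided 5% level and a true change of 0.5 SD.

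**Standard errors of the mean change.**
- Unpaired: s × sqrt(2/n)
- Paired: s × sqrt(2(1 − r)/n)
- Ratio: 1/sqrt(1 − r), which does not depend on n

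| Assumed r | 1/sqrt(1 − r) |
|---|---|
| 0 | 1.00 |
| 0.2 | 1.12 |
| 0.3 | 1/sqrt(0.7) = 1.20 |
| 0.5 | 1/sqrt(0.5) = 1.41 |
| 0.7 | 1/sqrt(0.3) = 1.83 |
| 0.8 | 1/sqrt(0.2) = 2.24 |
| 0.9 | 3.16 |

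Simulation (20,000 replicates) agrees: 1.42 and 2.24 at n = 18 for r = 0.5 and 0.8. If the ANOVA is run as repeated measures, it is the paired test and the ratio is 1.0 whatever r is.

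**Effect on the test.** From the same simulation:

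| n | Assumed r | Type I error, unpaired | Power, unpaired | Power, paired |
|---|---|---|---|---|
| 18 | 0.3 | 2.2% | 28% | 40% |
| 18 | 0.5 | 0.8% | 25% | 52% |
| 18 | 0.8 | below 0.1% | 17% | 89% |
| 9 | 0.3 | 2.4% | 14% | 21% |
| 9 | 0.5 | 1.0% | 10% | 26% |
| 9 | 0.8 | 0.1% | 6% | 55% |

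The unpaired type I error is below the nominal 5% throughout, so the error is conservative. The power columns are illustrative. They use one effect size and normal data, which suits a scale score better than the single 3-point family-communication item.

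**Which assessment is the baseline?** Time 3 is the last one scheduled for controls, 7 months after enrolment. A control enrolled in January of Year 2 reaches it about August of Year 2. The program is offered in July to September of Year 3, so that baseline would be about 11 to 13 months old at the offer. At the other end, a control enrolled in June of Year 3 would reach Time 3 about January of the following year, after the offer period. The gap between baseline and program start therefore cannot be assumed short or uniform.

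**Which outcomes have a pre value?** Program targets are measured at Times 1, 2 and 3, and quality of life at Times 1 and 3. Controls write a plan of action at Time 2. The measures section gives no time points for unmet needs or family relationships.

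**The case against.** The strongest reply is that the phrase is shorthand. The main analysis has two factors, condition and assessment. Among crossed-over controls condition drops out, and what remains is a one-factor repeated measures ANOVA. The next paragraph of Data Analysis names independent-samples t-tests when separate groups are meant. The plan also bases Cohen's d on changes and reports reliable change, so the authors think in within-person terms. This reading is plausible, and under it there is no inflation. The text does not settle the matter, however, and the same wording change is needed either way.

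It is also fair to say that no inflation factor can be taken from the documents. A range of 1.4 to 2.2 follows only if r lies between 0.5 and 0.8. Over r = 0.2 to 0.9 the range is 1.1 to 3.2.

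A reader might go further in two ways that the documents do not support.

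- *That the plan definitely discards the pairing and will wrongly show no benefit in controls.* The wording permits that analysis but does not require it. Whether a change would be missed depends on r, n and the true effect, none of which is given.
- *That each control's change from Time 1 to Time 2 is a ready untreated comparison.* Controls receive the tip sheets and information packet as their assigned condition, so the period is not a plain wait. Quality of life is not measured at Time 2 and the plan of action has no Time 1 value, so neither has a change over that period. For early enrollees, a 4-month change would be set against a Time 3-to-post interval of more than a year.

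**Conclusion.** The point holds as a defect of specification. The plan names a test which, taken literally, is wrong for paired data, and it does not define the baseline. The inflation of the standard error is conditional on an independent-groups analysis and on an assumed correlation: 1.20 at r = 0.3, rising to 2.24 at r = 0.8, and 1.0 if a repeated measures ANOVA was meant.

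The consequence is limited. The error could hide a change but would not produce spurious ones. It affects a secondary, uncontrolled analysis of at most 18 self-selected siblings and leaves the randomised comparison untouched. Correcting it restores precision only: even a paired analysis here cannot separate a program effect from time, repeat testing or the choice to take part.

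**What to change.** Replace the one-way ANOVA wording with a within-person analysis, either a paired t-test or a one-way repeated measures ANOVA (equivalent with two time points). Report the number of siblings, the mean change and its 95% CI for each outcome that has both a pre and a post value.

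State which assessment serves as the baseline. Time 3 is the last one scheduled for controls; report the time from the chosen assessment to program start, and say what is done for a sibling or outcome with no value at that point.

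If the change from Time 1 to Time 2 is shown beside the program-period change, present it as descriptive only, because written materials were provided in that period and the intervals differ.

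The cost is two or three sentences in the analysis section. No new data are needed if an existing assessment is used as the baseline. A fresh pre-program assessment would add data collection and is not required for this correction.

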## **Measures**

Siblings will complete all written measures unless indicated otherwise. Measures are organized according to baseline characteristics, treatment targets, and proximal outcomes expected to change as a function of program participation. Baseline characteristics related to the functioning of the adult with ASD (i.e., all except

demographics) are also considered longer-term outcomes that are expected to improve over time but which are not expected to change within the time frame of the proposed data collection. In the current work, baseline characteristics will be used to characterize the sample. In future, larger-scale work, these variables will be examined as possible moderators of treatment effectiveness.

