5. Broader Autism Phenotype (BAP) Characteristics in the Sibling. Sibling FORWARD program facilitators will rate each sibling's social pragmatic communication skills using the Adult Pragmatic Rating Scale after Session 1. This measure has been used to evaluate the communication of parents of individuals with ASD and is conceptualized as a marker of the BAP. Eighteen behaviors are rated on a 3-point scale with specific descriptors. Items query grammatical errors and speech complexity, verbal intonation, verbal behavior about own emotional state, organization and clarity of verbal communication, descriptive and emotional gestures, appropriateness of detail and references in communication, candidness of communication, mispronunciation and articulation, eye contact, range of facial expression, expressed empathy, and habitual laughter. This information will not be collected from control siblings.

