Acceptability (open trial and RCT): Qualitative data about perceptions of program usefulness and value collected during exit interviews with providers and participants will be evaluated using the qualitative methods outlined for Aim 1. Participant understanding of measures and procedures (open trial): Missing data and inconsistent response patterns on measures completed by siblings will be recorded. Data collection time will be calculated descriptively (mean, standard deviation, and range); participant burden associated with completing study measures will be captured qualitatively and summarized using content analysis. Enrollment and retention (RCT): Enrollment will be evaluated by calculating the number of eligible participants who chose to enroll in the trial. Descriptive statistics show the average number of sessions completed by participants and retention and follow-up rates. To assess selective attrition, we will evaluate the demographic and clinical characteristics of participants who completed the program versus those who did not using t-tests and chi squares. Adherence (RCT): Providers' fidelity to the manual will be assessed by evaluating video recordings of sessions against checklists of required components and calculating the percentage of required components that were present in each session; 20% of sessions will be coded for fidelity. Appropriateness of outcome measures (RCT): Psychometric properties of measures (alpha coefficients, means, SDs) and descriptive statistics of change scores from pre- to post-program time points (including confidence intervals) will be calculated.

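### The moderator analysis has no program-versus-control contrast, and BAP is not measured in controls, so it estimates predictors of change and completion rather than moderation

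*Combined protocol and SAP*

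**What the plan says.** Under Aim 3 of Data Analysis the plan states: "We will conduct a preliminary investigation of potential moderators of program effectiveness". It lists one sibling characteristic (BAP), four family characteristics (income, race/ethnicity, English as primary language, number of family members with ASD) and three characteristics of the adult with ASD (symptom severity, problem behaviors, functional independence). Two methods follow: "We will calculate correlations between these variables and change scores in primary outcome variables", and "independent samples t-tests between these variables and program completion status".

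BAP is item 5 under Baseline Characteristics: "Sibling FORWARD program facilitators will rate each sibling's social pragmatic communication skills using the Adult Pragmatic Rating Scale". The rating is made after Session 1, and the item ends: "This information will not be collected from control siblings".

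Two other places bear on the point. Under Aim 2, to assess selective attrition, the plan will "evaluate the demographic and clinical characteristics of participants who completed the program versus those who did not using t-tests and chi squares". The introduction to Measures says that in the current work the baseline characteristics serve to describe the sample, and then: "In future, larger-scale work, these variables will be examined as possible moderators of treatment effectiveness".

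**The concern.** A moderator of program effectiveness is a trait across which the program-control difference varies. Estimating that requires condition in the analysis. Condition appears only in the Aim 3 repeated-measures ANOVAs, which do not include the traits; the two moderator methods include the traits but not condition.

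Three misreadings are possible. A trait that predicts change equally in both arms may be reported as a moderator. A trait that works in opposite directions in the two arms may be missed, because the slopes cancel when the arms are pooled. A BAP correlation in the program arm may be read as moderation with no control comparison behind it. The timeline ends with a grant application for a larger trial, so a mislabelled signal could influence which moderators that trial pursues.

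**Working it through.** **What each planned statistic estimates**

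- *Trait-by-change correlation.* It has no condition term, and the plan does not say whether arms are pooled or separate. It estimates how the trait relates to change.
- *t-test by completion status.* Only program-arm siblings have a program to complete before the randomized outcomes are in; Control Condition offers it to controls afterwards. The test estimates how completers differ from non-completers, a comparison already planned under Aim 2.
- *BAP.* It is rated by program facilitators after Session 1 and has no control values. The control-arm slope, and therefore the difference in slopes, cannot be estimated from the planned data. This needs no simulation.

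**Illustration of size**

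The plan gives no alpha, power or decision rule for this analysis, so there is no figure to reproduce. The allocation of 18 and 18 comes from Procedures, RCT. Everything else is assumed: two-sided alpha 0.05, standard normal trait, change SD 1 within arm, full follow-up, and a mean program-control difference in change, d, from 0 to 0.8 SD. The rates come from 40,000 simulated trials per scenario.

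Same trait-change correlation r in both arms (no moderation), percentage of trials significant:

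| r | Pooled correlation (n = 36) | Program arm alone (n = 18) | Condition-by-trait interaction |
|---|---|---|---|
| 0.1 | 8-9 | 7 | 5 |
| 0.2 | 19-22 | 12-13 | 5 |
| 0.3 | 38-44 | 23 | 5 |
| 0.4 | 62-70 | 39 | 5 |
| 0.5 | 83-89 | 59 | 5 |

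The program-arm column is all that can exist for BAP.

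The Fisher z approximation agrees. Significance probability ≈ Φ(atanh(r) × √(n − 3) − 1.96).

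- Pooled, r = 0.5, d = 0: Φ(0.549 × √33 − 1.96) = Φ(1.20) = 0.88.
- Program arm, r = 0.5: Φ(0.549 × √15 − 1.96) = Φ(0.17) = 0.57.
- With a mean difference d, the pooled correlation shrinks to r/√(1 + d²/4). For r = 0.5 and d = 0.8 this is 0.5/√1.16 = 0.464, giving Φ(0.503 × √33 − 1.96) = Φ(0.93) = 0.82.

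Missed moderation: with slopes +0.4 (program) and −0.4 (control), the pooled correlation is significant in about 7% of trials and the interaction in 66%.

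With 15 per arm (assumed attrition) and equal slopes, the pooled correlation is significant in 17-19% at r = 0.2 and 54-61% at r = 0.4; the interaction stays at 5%.

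**Precision and multiplicity of the correct analysis**

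- Median 95% CI half-width for the interaction, over r = 0 to 0.5: 0.72 down to 0.62 SD of change per SD of trait at 18 per arm, and 0.80 down to 0.70 at 15 per arm.
- Power for slopes of 0.5 (program) against 0 (control): 31-32% at 18 per arm, 26% at 15 per arm. Fisher z check at 18 per arm: Φ(0.549/√(2/15) − 1.96) = Φ(−0.46) = 0.32.
- The simulation does not represent race/ethnicity, English as primary language or the 3-point communication item. Leaving these out, 5 traits × 5 program targets (an assumed outcome set) gives 25 pairs. With no moderation, 25 × 0.05 = 1.25 false signals are expected, and 1 − 0.95²⁵ = 0.72 is the chance of at least one if the tests were independent. Counting all 7 non-BAP traits and 6 targets gives 42 pairs, 42 × 0.05 = 2.1 and 1 − 0.95⁴² = 0.88; correlation among traits and outcomes lowers the last figure.

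**The case against.** The strongest defence is that this is declared preliminary work in a 36-family pilot. Design Considerations leaves increased examination of moderators to larger trials, and no main conclusion depends on it. That stands and limits the severity. It excuses imprecision, however, not a method aimed at a different quantity.

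A second point is that the high rates above assume pooled arms, equal slopes and a significant correlation being read as moderation, none of which the plan states. That is fair, and the figures are illustrative for that reason. Running the correlations by arm would also comply with the text, but no comparison between arms is planned, and BAP would still have no control values.

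Third, the interaction gains little in one plausible case. If a trait relates to change only in the program arm (0.5 against 0), the pooled correlation is significant in 28-33% of trials and the interaction in 31-32%. This also stands, and is why the interaction should be reported as an estimate with an interval and not as a test.

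Fourth, predictors of completion are useful feasibility information, and their overlap with Aim 2 is repetition, not error. Only their placement under moderators is wrong. Likewise, the Measures text and Aim 3 differ in wording more than in substance.

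Controls who later take the program might be rated for BAP, but no such rating is planned; it would come after the randomized outcomes and only in those who opt in.

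**Conclusion.** The concern holds. Followed exactly, the plan estimates predictors of change and of completion under the name of moderators, and moderation by BAP is not estimable from the planned data. These conclusions follow from the text alone.

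How often a non-moderator would look like one depends on how strongly it predicts change: from 8-9% at r = 0.1 to 83-89% at r = 0.5 under the stated assumptions, which do not extend to categorical traits. The consequence for the trial is modest. This should be corrected, but it does not threaten the main Aim 3 comparison.

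**What to change.** 1. For traits measured in both arms, and outcomes with a Time 1 value, regress the change score on condition, trait and condition-by-trait. Report each interaction estimate with its 95% CI as exploratory, and make no significance-based moderator claim, given the number of trait-outcome pairs.
2. For categorical traits, report the program-control difference in change within each category where cell sizes allow.
3. Take BAP off the moderator list and report it as a predictor of change within the program arm.
4. Describe the completion-status t-tests as predictors of completion, in line with Aim 2.
5. Add a phrase to the introduction of Measures acknowledging the exploratory analysis in this trial, so that it agrees with Aim 3.

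The minimum alternative is to relabel the whole analysis as exploratory predictors of change and completion, with no moderation claim.

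The cost is analysis-plan wording only: the data are already planned and the main Aim 3 model is unchanged. The downsides are wide intervals, low power, some categories too small to estimate, and no statement on moderation by BAP.
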